## 7. DISCONTINUATION OF STUDY AND SUBJECT DISCONTINUATION OR WITHDRAWAL

A premature discontinuation will occur if a subject who signs the informed consent form (ICF) and is randomized ceases participation in the study, regardless of circumstances, before the completion of the protocol-defined study procedures.

### 7.1. Subject Discontinuation/Withdrawal from the Study

- A subject may choose to withdraw from the study at any time at her own request or may be withdrawn at any time at the discretion of the investigator or Sponsor for safety, behavioral, compliance, or administrative reasons.
- If a subject withdraws consent for disclosure of future information, the Sponsor or designee may retain and continue to use any data collected before such a withdrawal of consent.
- If a subject withdraws from the study, she may request destruction of any blood or urine samples taken and not tested, and the investigator must document this in the site study records and communicate this request to the Sponsor study team so that appropriate measures may be taken to ensure destruction of the materials.
- Subjects who withdraw from the study will not be replaced (enrollment accounts for a predetermined dropout rate).

The Week 24/Exit Clinic Visit (Visit 8) assessments as specified in the Schedule of Assessments ([Section 1.3](#)) will be completed when a subject withdraws or is withdrawn from the study, if possible.

Reasons for discontinuation from the study include the following:

- AE
- Lack of efficacy
- Noncompliance
- Withdrawal of consent
- Lost to follow-up
- Physician decision
- Protocol deviation
- Pregnancy
- Death
- Administrative issues (eg, site closure)
- Other

## 7.2. **Lost to Follow-Up**

Should a subject fail to attend a required study visit, the site should attempt to contact the subject and re-schedule the missed visit as soon as possible. The site should also counsel the subject on the importance of maintaining the assigned visit schedule and ascertain whether or not the subject wishes to and/or should continue in the study based on previous non-compliance. In cases where the subject does not return for the rescheduled visit or cannot be reached to reschedule the missed visit, the site should make every effort to regain contact with the subject so that they can appropriately be withdrawn from the study with a primary reason of “Lost to Follow-up”, including at least three documented attempts to contact the subject (ie, phone, email, or certified letter). Efforts to establish the possible reason for discontinuation should be documented.

## 7.3. **Early Study Termination**

The Sponsor reserves the right to terminate the study for any reason. The study may be terminated early if the extent (incidence and/or severity) of emerging effects/clinical endpoints is such that the risk/benefit ratio to the study population as a whole is unacceptable. In addition, further recruitment in the study overall or at a particular study site may be stopped due to insufficient compliance with the protocol, Good Clinical Practice and/or other applicable regulatory requirements, procedure-related problems or the number of discontinuations for administrative reasons is too high.

## 8. STUDY ASSESSMENTS AND PROCEDURES

Study procedures and their scheduled timepoints are summarized in the Schedule of Assessments ([Section 1.3](#)). Site personnel should note the following:

- Protocol waivers or exemptions are not allowed; however, subjects who fail to meet eligibility criteria may be rescreened once, as appropriate (See [Section 5.4](#)). Any notable protocol deviations should be noted and raised to the Sponsor's or designee's attention.
- Immediate safety concerns should be discussed with the Sponsor's designated Medical Monitor immediately upon occurrence or awareness to determine if the subject should continue or be discontinued from the study.
- Adherence to the study design requirements, including those specified in the Schedule of Assessments, is essential and required for study conduct.
- Evaluations should be performed by the same evaluator throughout the study whenever possible.

### 8.1. Screening Procedures

Screening procedures can commence once the informed consent and data authorization/protection form have been obtained. Screening will be considered to have started at the time of the first screening activity or procedure and completed when all the required inclusion/exclusion criteria have been met and the subject is randomized. Screening procedures should be completed as soon as possible, with a maximum of a 35-day window. There is no minimum duration for screening procedures and randomization as long as the subject undergoes the required protocol-defined assessments at each respective visit and is fully evaluated for eligibility based on the clinical judgment of the investigator.

All screening evaluations must be completed and reviewed to confirm that potential subjects meet all eligibility criteria. The investigator will maintain a screening log to record details of all subjects screened and to confirm eligibility or record reasons for screening failure, as applicable. Inclusion and exclusion criteria will be reviewed by the investigator or qualified designee at the Screening and Randomization Visits (Visits 1 and 2, respectively).

For screen failure procedures, see [Section 5.4](#).

#### 8.1.1. Informed Consent

Documented consent must be obtained from each potential subject prior to participating in any study procedures. Refer to [Section 10.1.3](#) for a detailed description of the informed consent process, including the voluntary nature of clinical study participation and the subject's right to withdraw consent at any time.

### **8.1.2. Assignment of Subject Number**

All subjects who sign the ICF will be assigned a unique subject number by IWRS. This number will be used to identify the subject throughout the study. Subjects who are rescreened will be assigned a new subject number. If a new subject number is assigned, the subject will be linked to both subject numbers.

### **8.1.3. Medical History**

A medical history will be obtained by the investigator or qualified designee. Medical history will include all chronic and ongoing conditions, regardless of year diagnosed, surgical history, and substance abuse history. All events occurring after the subject signs the ICF will be recorded as adverse events.

### **8.1.4. Demographics**

Demographic data collection will include sex, age, race, and ethnicity.

### **8.1.5. Prior and Concomitant Medications**

Any prior OAB medications (over the past 3 years), any other prior medications used up to 6 months before the Screening Visit, as well as ongoing (concomitant) medications will be recorded beginning at the signing of the ICF and continuing until the Week 48 Safety Follow-up assessment.

If additional OAB medication(s) is used or procedures are performed at Week 24 or after (see [Section 6.9.2](#)), these must be recorded in the appropriate eCRF form.

## **8.2. Efficacy Assessments**

Efficacy assessments will be collected as outlined in the Schedule of Assessments ([Section 1.3](#)) in the form of a 3-day Bladder Diary. Information collected in the diaries will be used for assessment of the exploratory efficacy endpoints related to the number of UUI episodes, micturitions, urgency episodes, and UI episodes per day as well as one 24-hr period to record volume voided of urine.

Subjects will complete questionnaires at the site during the study visits specified in the Schedule of Assessments ([Section 1.3](#)) before vital signs and blood draws to assess subject-perceived symptom relief and health-related quality of life. The patient-reported outcome (PRO) questionnaires are provided in [Section 10.9](#). Urodynamic parameters will also be measured. Additional information on the Bladder Diary, questionnaires, and urodynamic parameters is provided below.

### 8.2.1. Bladder Diaries

The Bladder Diary is used by subjects to record the frequency of daily OAB symptoms including all micturitions, urgency, UUI, UI, and main reason for incontinence, and volume voided per micturition (over one 24-hour period) by selecting the respective box for each symptom/event occurring during the course of a given day and night.

Bladder diary must be completed by subjects for any 3 consecutive days in the 7 days prior to the visit (for screening only, it can be completed for 3 consecutive days at any time during the screening and randomization period); total volume voided must be collected for one 24-hour period during the 3-day diary collection period. Please refer to [Section 10.7](#) for washout periods for prohibited medications. The Screening Bladder Diary should be started only after washout of prohibited medications is complete.

A “Diary Day” is defined as the time between when the subject gets up for the day each morning (ie, the time the subject got up for the day yesterday to the time the subject got up for the day today; approximately a 24-hour period).

To be eligible for the study, subjects must have a minimum of 3 consecutive Diary Days during the screening and randomization period (at any time during the period) and be capable in the investigator’s opinion of maintaining compliance with the diary requirements, including the measurement and recording of urine volume, as required throughout the course of the study.

At all study visits, the site staff should inquire whether the subject had any difficulties with the diary and address any questions subjects may have. Instructions for proper completion of the diary should be re-reviewed. Subjects will be trained to enter data immediately following each event (in real time) and to input data from any “missed” events as soon as they are able. They will review and confirm that data from all events occurring within the preceding Diary Day (approximately 24 hours) have been entered at a consistent time each morning (eg, upon getting up for the day).

Responses to the Bladder Diary will be reviewed by the site staff to assess whether subjects are capable of completing the diary and if subjects meet eligibility criteria. The daily averages for micturitions, urgency episodes, UUI episodes, and UI episodes will be calculated as average of the total by the number of events on Diary Days. Subjects who do not meet the OAB entry criteria will be excluded from the study.

Note that diaries must be completed within 7 days prior to the protocol-defined timepoint regardless of any visit delay due to COVID-19. If a visit will be delayed per the COVID-19 mitigation window, the site should contact the subject to ensure that the diary completion occurs per the protocol-defined timepoints and not within the 7 days prior to the COVID-delayed visit.

More detailed instructions on the diary and instructions for use are provided in the appropriate study manual.

### 8.2.2. Patient-Reported Outcomes

The subject's perception of the level of impairment in functioning and well-being associated with the symptoms of OAB will be assessed using subject-completed questionnaires as specified below. Questionnaires should be administered prior to the subject undergoing any invasive procedure for any study visit, prior to vital signs measurement, and prior to study treatment at the Day 1 Visit. The versions of the questionnaires provided in the protocol are samples and will be replaced. Additional information on administering and completing these questionnaires is outlined in [Section 10.9](#). These include the following questionnaires:

- Urinary Incontinence-Specific Quality-of-Life Instrument (I-QOL) total summary score
- OAB Questionnaire (OAB-q) score
- Patient Global Impression of Change (PGI-C) scale score

Examples of each of the PRO measures are provided in [Section 10.9](#).

### 8.2.3. Urodynamic Parameters

Urodynamic assessments will only be performed at baseline after confirmation of subject eligibility during the Randomization Visit (Visit 2) prior to performing the actual randomization procedure. A historical urodynamic study, performed no more than 90 days prior to the first day of screening, may serve as the baseline urodynamic assessment if the criteria detailed below are satisfied.

Historical urodynamic study may be substituted for the baseline urodynamic assessment, if the following 3 criteria are met:

- Historical urodynamic study was obtained no more than 90 days prior to the first day of screening
- Historical urodynamic results are available for evaluation by the central reader
- Subject was not being treated with any OAB medication or had discontinued OAB treatment in accordance with Exclusion Criterion #3

In case of subjects being rescreened when a historical urodynamic assessment was used for the original screening, it will NOT need to be repeated if rescreening still occurs within 90 days of the valid historical urodynamic assessment. If rescreening occurs more than 90 days since the historical urodynamic assessment, a new urodynamic test will need to be performed prior to randomization as the baseline assessment.

At Week 12, all subjects will undergo a second urodynamic assessment.

Conduct of urodynamic testing will be standardized across all study sites and will be according to ICS standard guidelines [Homma 2002].

Urodynamic data will be reviewed by an independent central reviewer to determine final values for analysis purposes for the parameters listed below. The investigator, physician subinvestigator, or trained technician will perform urodynamic procedures on each subject, then interpret and record the results on the calculation worksheet. The worksheet and the tracings should be signed and dated by the investigator or physician subinvestigator. A test trace will be submitted by each site. A copy of the worksheet, along with the printed tracings will be submitted to the central reader. Only the central reader's interpretation of the results will be recorded in the eCRF for final analysis. Study sites will not typically be informed of any differences between their urodynamic values and the urodynamic values determined by the central reviewer. However, study sites may receive feedback if persistent methodological issues arise per the central urodynamic reader. Note that the investigator does not need to wait for the results of the baseline urodynamic assessment to rule out bladder outlet obstruction if there are no other signs or symptoms of obstruction, in the investigator's assessment, including elevated PVR volume (see [Exclusion Criterion 13](#)).

The following urodynamic parameters are to be measured:

- Cystometric volume at 1st sensation to void (FSV)
- Maximum cystometric capacity (MCC)
- Maximum detrusor pressure during the storage phase (corrected PdetMaxStorage)
- Presence/absence of the first involuntary detrusor contraction (IDC) and, if present:
  - Volume at first IDC (Vol@1stIDC)
  - Maximum detrusor pressure during the first IDC (corrected Pdet@1stIDC)

Additional related instructions will be provided in the appropriate study manual.

### 8.3. Pharmacokinetic Assessments

Urine and blood samples for *hSlo* cDNA assessment will be collected pre-treatment from subjects on Day 1 (Visit 3; treatment administration), 2 hours ( $\pm$  1 hour) post-treatment on Day 1, Week 6 follow-up clinic visit (Visit 5), and Week 24 follow-up clinic/exit visit (Visit 8). If a specimen(s) is still positive at Week 24, per the clinical discretion of the investigator, a subject may be instructed to return at Week 36 (Visit 9) and, if necessary, Week 48 (Visit 10) until the specimen(s) result is negative for *hSlo* cDNA. Pharmacokinetic assessment is to be performed at the Early Withdrawal Visit for subjects who withdraw early from the study. Information on procedures for collection, handling, storage, and shipping the samples will be provided in a separate study manual.

## 8.4. Safety Assessments

Planned timepoints for all safety assessments are provided in the Schedule of Assessments ([Section 1.3](#)). Immediate safety concerns should be discussed with the Sponsor's designated Medical Monitor immediately upon occurrence or awareness to determine if the subject should continue or discontinue study drug.

### 8.4.1. Vital Signs

- Vital signs, including blood pressure (mmHg), heart rate (by pulse; beats per minute), respiration rate (breaths per minute), and body temperature (°C) will be assessed at the timepoints specified in the Schedule of Assessments ([Section 1.3](#)).
- Blood pressure and pulse will be measured after the subject has been resting in a seated position for 5 minutes, after questionnaires have been administered, and before blood draws.
- Blood pressure measurements will be taken on the same arm and by the same site staff throughout the study, if possible.
- The same method for assessing temperature should be used at all visits for a particular subject.
- Body weight will be measured with subjects in street clothing with jacket/coat and shoes removed, using the same scale throughout the study, if possible.
- Standing height will be measured at screening only.

### 8.4.2. Physical Examinations

Brief physical examinations will include examination of the heart, lungs, abdomen, and visual pelvic examination. In addition, any organ system in which a previous abnormality was noted during screening or a subject has a complaint or AE will be examined.

### 8.4.3. Electrocardiograms

A 12-lead ECG will be performed in the supine position at the visits specified in the Schedule of Assessments ([Section 1.3](#)) using an ECG machine that automatically calculates the heart rate and measures PR, QRS, QT, and QTc intervals. ECGs will be read by trained personnel at the study site or appropriate delegates who are medically qualified.

### 8.4.4. Post-Void Residual Volume

The volume of urine that remains in the bladder after voiding (PVR) is an objective measurement that may serve as a proxy for impaired ability to void. The physician should assess subjects with an increase in PVR volume to determine whether an AE should be reported. (Refer to [Section 8.5.6](#) for additional information on reporting AEs of urinary retention associated with increased PVR.)

The PVR assessment will be performed via ultrasound at the visits indicated in the Schedule of Assessments (Section 1.3). Note that since Visit 7 (Week 18) is a telephone (or other virtual technology) visit, subjects will not be seen in the clinic for 12 weeks between Visit 6 (Week 12) and Visit 8 (Week 24). Should the investigator identify a clinically relevant elevation in PVR volume at Visit 6, an unscheduled clinic visit should be performed at the investigator's discretion to repeat the urine PVR assessments and urine dipstick. All efforts should be made to ensure the same device and operator are used for all PVR volume measurements for individual subjects.

#### **8.4.5. Clean Intermittent Catheterization**

The following guidance should be used for the initiation of CIC in this study. Sterile, single-use intermittent catheters should be used. Indwelling catheters should not be used in this study.

##### *Initiation of Clean Intermittent Catheterization*

As described above in the PVR section, CIC should be initiated per protocol when one of the following criteria is fulfilled:

- PVR is  $\geq 350$  mL at any posttreatment visit, regardless of whether the subject reports associated symptoms
- PVR is  $\geq 200$  mL and  $< 350$  mL and the subject spontaneously reports associated symptoms (ie, voiding difficulties, sensation of bladder fullness) that in the opinion of the investigator requires CIC.

The following will occur when initiating CIC (for elevated PVR as described above):

1. CIC is implemented and the subject should be instructed to perform CIC using sterile, single-use catheters (which will be provided to the subject)
2. An adverse event of urinary retention is recorded
3. Central laboratory urine analysis and culture/sensitivity are performed as per routine requirements at each study visit
4. The subject will be seen for a follow-up visit 1 week later where the PVR, associated symptoms, central laboratory urine analysis and culture/sensitivity will be reassessed. The investigator will determine whether the subject can then be followed per protocol scheduled study visits or whether additional follow-up visits should occur.

Once CIC is initiated, the status of CIC use should be documented in the subject record at each visit (ie, use/nonuse).

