### **8.5.6. Adverse Events of Special Interest**

Selected nonserious and SAEs will be reported as AESIs. AESIs that also meet the definition of an SAE must be reported as described in [Section 10.3](#).

AESIs for this study include:

- Adverse events consistent with urinary retention
  - An AE of urinary retention should only be recorded when a subject has a raised PVR that requires intervention with CIC or temporary placement of a urinary catheter according to the following criteria:
    - a) subject has a PVR of  $\geq 350$  mL (regardless of symptoms), OR
    - b) subject has a PVR  $\geq 200$  mL and  $< 350$  mL and the subject reports associated symptoms, ie, sensation of bladder fullness or inability to void despite persistent effort, that in the investigator's opinion require CIC.

Note: An AE of residual urine volume should be recorded if, in the investigator's opinion, the raised PVR is clinically significant but does not fulfill the above definition for urinary retention.

- Adverse events suggestive of cystitis or UTI
  - An AE of UTI will be recorded if both the following criteria are fulfilled, regardless of subject symptoms:
    - a) a positive urine culture result with a bacteriuria count of  $\geq 10^5$  CFU/mL (ie,  $100 \times 10^3$  CFU/mL)
    - b) leukocyturia of  $\geq 5$  /hpf

If a subject meets the criteria for the definition of a UTI, the investigator will record whether the UTI was "symptomatic" or "asymptomatic" on the AE eCRF.

Note: If urinalysis/culture results are reported which, in the opinion of the investigator, are considered clinically significant but do not fulfill the above definition of a UTI, the findings should be recorded as AEs (eg, bacteriuria, leukocyturia).

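### For PVR of 200 to below 350 mL, Protocol 8.4.5 and 8.5.6 use different symptom lists, so one narrow group of subjects is a urinary-retention AE under one section and not under the other

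*Protocol*

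**What the plan says.** Protocol 8.4.5 (Initiation of Clean Intermittent Catheterization) gives two triggers for CIC. The first is PVR of 350 mL or more, with or without symptoms. The second is PVR of at least 200 and below 350 mL where "the subject spontaneously reports associated symptoms (ie, voiding difficulties, sensation of bladder fullness" and CIC is, in the investigator's judgement, needed. Among the steps that follow once CIC starts, the second reads "An adverse event of urinary retention is recorded", with no further condition.

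Protocol 8.5.6 defines the retention AESI. It opens restrictively: "An AE of urinary retention should only be recorded when a subject has a raised PVR that requires intervention with CIC". Temporary catheterization is named as an alternative intervention, and listed criteria follow. The PVR cut-offs are the same as in 8.4.5. In the lower band, however, the qualifying symptoms are "sensation of bladder fullness or inability to void despite persistent effort, that in the investigator's opinion require CIC". A note adds that a raised PVR which the investigator considers clinically significant, but which misses this definition, is recorded as an AE of residual urine volume.

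Three other places bear on the point. Protocol 8.4.4 refers the reader to 8.5.6 for reporting retention. SAP 7.2 identifies AESIs from a tick box on the AE form and cites 8.5.6 for the criteria. Protocol 4.2 lists retention and urinary tract infection AEs, as the protocol defines them, among the parameters to be closely monitored, which presupposes a single definition.

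**The concern.** Retention is one of only two AESI types in this trial; the other is cystitis or urinary tract infection. Both sections introduce their symptom lists with a term meaning that is, so each list reads as complete rather than as examples. One section orders the AE to be recorded, and the other restricts it to narrower grounds. For some subjects a site cannot follow both.

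At stake is whether the same clinical course is coded the same way across up to 25 sites and three treatment groups. The choice affects the preferred term, the AESI summaries (SAP Tables 14.3.1.11 and 14.3.1.12 and Listing 14.3.2.9), and whether the 72-hour deadline for nonserious AESIs in Protocol 8.5.1 applies. With 26 or 13 subjects per group and an event that may be rare, a single coding decision shows in the table.

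**Working it through.** The plan states no figure on this point, so the main check is a comparison of the two sections.

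| Element | Protocol 8.4.5 | Protocol 8.5.6 |
|---|---|---|
| PVR 350 mL or more | Qualifies without symptoms | Qualifies without symptoms |
| PVR 200 to below 350 mL, symptoms | Voiding difficulties; bladder fullness | Bladder fullness; inability to void despite sustained effort |
| How symptoms come to light | Spontaneously | Reported, not further qualified |
| Investigator judges CIC necessary | Yes | Yes |
| Consequence | CIC starts; retention AE recorded | Retention AE only if the criteria are met |

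Five kinds of subject, with CIC judged necessary where PVR is below 350 mL:

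1. PVR 350 mL or more: retention AE under both.
2. PVR 200 to below 350 mL, fullness volunteered: retention AE under both.
3. Same band, complete inability to void volunteered: retention AE under both, since inability is also a voiding difficulty.
4. Same band, a lesser voiding difficulty volunteered (for example hesitancy at PVR 250 mL), no fullness: retention AE under 8.4.5, not under 8.5.6. **This is the conflict.**
5. Same band, fullness or inability to void disclosed only on questioning: 8.5.6 allows the AE, while 8.4.5 does not trigger CIC. Because 8.4.5 does not forbid the AE, this is a mismatch between recording and CIC initiation, not a second AE conflict.

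Size of one reclassified subject, using the planned arm sizes (26 active and 13 placebo per cohort, Protocol 4.1):

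- Active arm: 1/26 = 3.8 percentage points.
- Placebo within one cohort: 1/13 = 7.7 points.
- Placebo pooled at the final analysis (Protocol 9.1): 1/(13 + 13) = 1/26 = 3.8 points.
- Moving from 0/26 to 1/26 changes the exact (Clopper-Pearson) 95% interval from 0 to 13.2% into 0.1 to 19.6%. The first upper limit is 1 − 0.025^(1/26) = 13.2%.

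Chance of at least one type 4 subject among 26 active subjects is 1 − (1 − p)^26, where p is the proportion of such subjects. The documents give no p, so these values are assumptions:

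| Assumed p | Chance of at least one |
|---|---|
| 1% | 23% |
| 2% | 41% |
| 5% | 74% |
| 10% | 94% |

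The only related statement in the documents is in Protocol 2.3.2, that no urinary retention was seen in earlier work. That gives no support to the upper end of this range.

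**The case against.** The strongest reply is that the protocol already says which section governs. Protocol 8.4.4, immediately before the CIC section, sends retention reporting to 8.5.6, and SAP 7.2 does the same for AESI criteria. Section 8.4.5 presents itself as guidance on starting CIC. This lowers the standing of 8.4.5 as a definition, but its second step still orders a retention AE outright, and a site following that list would record one.

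The second reply is that the group is narrow and not hidden, and it stands. Discordance needs the 200 to below 350 mL band, a voiding difficulty short of inability, no fullness, and CIC judged necessary, all together. SAP 7.7 tabulates PVR with that band as a category, and SAP 7.8 summarizes CIC start and duration by arm. SAP 7 plans no inferential safety testing.

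A reader might infer that the conflict could sway the decision to go from 24 to 48 mg. The documents do not support that. The Data and Safety Monitoring Board (DSMB) reviews all unblinded Cohort 1 safety data to Week 6, no section makes AESI or retention counts an escalation criterion, and details are left to its charter.

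A reader might also see a flat contradiction over catheters, because 8.4.5 says "Indwelling catheters should not be used in this study" while 8.5.6 accepts temporary catheter placement as a qualifying intervention. That is weaker. An AE definition may capture a catheter placed outside the guidance, and 8.5.6 does not say the temporary catheter is indwelling. It needs clarifying, no more.

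Finally, 8.5.6 says should only, not must not, and the fallback to residual urine volume depends on the investigator's view of clinical significance. The subject may fall there; it is not certain that she does.

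**Conclusion.** The inconsistency is real and in the current text: a type 4 subject cannot be coded in line with both sections. Its reach is one narrow band, where each affected subject shifts a reported retention rate by 3.8 points (active arm or pooled placebo) or 7.7 points (single-cohort placebo). These figures assume the planned arm sizes. How many such subjects there would be is unknown.

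The practical effect is on coding, the AESI tables and reporting speed. It does not make the subject disappear from the safety outputs, and it cannot be shown to affect dose escalation. It merits correction because the correction is cheap and the AESI count should mean the same thing at every site. No view is taken on which symptom wording is clinically right.

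**What to change.** - Reconcile Protocol 8.4.5 and 8.5.6 so that one symptom list and one wording on spontaneous reporting govern both the start of CIC and the recording of the retention AE and AESI. The sponsor chooses the wording.
- State how temporary catheter placement in 8.5.6 sits with the indwelling-catheter statement in 8.4.5. In the same edit, correct the remark in 8.4.5 that its criteria were described in the PVR section, since 8.4.4 does not contain them.
- In SAP 7.2, add a cross-check of the AESI tick box against recorded PVR category and CIC use, and query mismatches. The SAP already summarizes both items. Deriving the AESI from symptoms should not be promised, because nothing in the documents shows that symptoms, or whether they were volunteered, are coded on the case report form.

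The cost is a wording change, a short site memo, one programmed check, and a brief blinded re-check of events already recorded. If DSMB tables fall under the separate analysis plan that the protocol allows for, the check would have to be added there too.
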